In clinical practice, there is no a universally easy and reliable test for the diagnosis of EPI. Gold standard diagnosis implies direct tests or 72-hour fecal fat quantification. However, their clinical applicability is limited. Valid alternatives such as fecal elastase-1 and C-labeled mixed triglyceride breath test assessing exocrine pancreatic function have gained special interest and wide use for their availability, cost and ease of application. Based on fecal elastase-1, EPI has been reported at 26.5%, 26.1% and 9.4% for a follow-up of <12months, 12-36months and >36months, respectively. Recent evidence suggests an increasing importance of the pancreas-intestinal axis in pancreatic pathology given the central role of the pancreas in controlling metabolism via its exocrine and endocrine pancreatic functions, possibly due to bacterial metabolites as short-chain fatty acids, immune modulation and pancreatic excretion of antimicrobials. Changes in gut microbiota have been more documented for pancreatic cancer and type 1 diabetes mellitus. Recently, [ZhHeLiCaHuLi19] showed that severe acute pancreatitis can also course with gut dysbiosis by decreased Firmicutes and Bacteroidetes and increased Protobacteria. However, the presence and implications of gut dysbiosis associated with acute pancreatitis and EPI following acute pancreatitis increasing risk of gut-derived infection, remains unclear. In recent years, efforts have been dedicated to find early predictors, alone or in association, of severity, organ dysfunction, and development of complications in patients with acute pancreatitis. In fact, our study group has also been dedicating itself to this thematic, having carried out studies and reflections with publications in international and national journals, identifying C-reactive protein (CRP), red cell distribution width (RDW) and RDW to total serum calcium ratio, as main early predictors (at admission of patients and within the first 24 hours of hospitalization) of severity in acute pancreatitis. However, no single biomarker or score demonstrated high accuracy in early prediction of severity or prognosis of acute pancreatitis to be used in clinical practice and, additionally, there are no studies on early predictors in the development of the EPI complication after acute

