pancreatitis. Important immunological changes, which may become biomarkers, have been described as associated with severe acute pancreatitis, such as interleukin(IL)-6, IL-8, IL- 10 and CRP. Recent studies have shown that IL-6  $\geq 28.90$ pg/mL in the first 48 hours (sensitivity:62.9%; specificity:80.0%), and the growth differentiation factor(GDF)-15  $> 3183.36$ pg/mL (sensitivity:89.5%; specificity:76.9%), pentraxin(PTX)-3  $> 1.05$ pg/mL (sensitivity:85.0%; specificity:88.0%) and hepatocyte growth factor(HGF)  $> 3020.1$ pg/mL (sensitivity:60.0%; specificity:92.8%) at admission were good predictors of severity in acute pancreatitis. However, there are no data on the main immunological changes associated with the development of EPI following acute pancreatitis. Pancreatic enzyme replacement therapy (PERT), the only treatment currently available for EPI secondary to other causes than acute pancreatitis, has benefit in EPI

secondary to chronic pancreatitis, post-pancreatic surgery and non-resectable pancreatic cancer. However, its use in EPI following acute pancreatitis lacks clinical evidence, needs further studies and its routine application in clinical practice is currently not recommended. Some studies have been shown improvement in survival of patients with EPI

secondary to severe or necrotizing acute pancreatitis and patients undergoing necrosectomy. When to start PERT and for how long to obtain clinical and nutritional benefits and the reversal of gut dysbiosis and immunologic changes in EPI following acute pancreatitis remain to be elucidated. Future prospective studies addressing these key issues are indispensable to determine the prevalence of EPI following an acute pancreatitis event and its predictors, as well as a double blind randomized placebo-controlled trial to assess the impact, efficacy and safety of PERT and its repercussions on gut microbiota, immunological status, clinical and nutritional course and patients' quality of life. In the future, new therapeutic targets may be explored in EPI following acute pancreatitis, such as manipulation of gut microbiota including prebiotics, probiotics, symbiotics and perhaps fecal microbiota transplantation and probably targeted immunotherapies. PERT and these new therapies could be applied to all patients after acute pancreatitis or in high-risk groups, including EPI.

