### **B. Objectives**

#### Primary objectives

- To determine the prevalence and duration of EPI following acute pancreatitis, and analytical and nutritional biomarkers related to the development of this complication;
- To evaluate when to start, the efficacy, safety and the duration of PERT in patients with EPI following acute pancreatitis;
- To assess changes in gut microbiota in EPI following acute pancreatitis and response to PERT;
- To assess changes in immunologic response in EPI following acute pancreatitis and response to PERT;
- To assess quality of life in EPI following acute pancreatitis and response to PERT.

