#### Secondary objectives

- To determine the prevalence and biomarkers associated with the development of endocrine pancreatic insufficiency following acute pancreatitis (type 3 diabetes mellitus, including new-onset pre-diabetes and/or diabetes mellitus);
- To evaluate changes in gut microbiota according to acute pancreatitis severity;
- To evaluate immunological changes according to acute pancreatitis severity.

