Randomization of patients with EPI following acute pancreatitis for PERT vs placebo. The efficacy, safety and compliance of PERT will be evaluated at 1 (for adjusting PERT dose) and 6 months after PERT start.

Phase 3: Analysis of gut microbiota and assessment of quality of life, and the impact of PERT on clinical and nutritional course, gut dysbiosis and patients' quality of life (at the diagnosis of acute pancreatitis, EPI and after PERT). Evaluation of richness, diversity and uniformity of gut microbiota by DNA sequencing

using the hypervariable region of the 16S rRNA gene. Assessment of quality of life using validated Portuguese versions of SF-36 and QLC-C30-V.3 Assess of PERT impact on clinical and nutritional course, gut dysbiosis and patients' quality of life.

Phase 4: Analysis of immunological changes and the impact of PERT on clinical and nutritional course and immunological status (at the diagnosis of acute pancreatitis, EPI and after PERT). Evaluation of immunological changes through the study of cell populations by flow cytometry (CD4+, CD8+, B-cell, T-cell, natural killer cells, cells ratio) and cytokines, chemokines and growth factors by xMAP/Luminex. Assess PERT impact on clinical and nutritional course and immunological changes.

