#### D.4. Statistical analysis

Using of Statistical Package for the Social Sciences (SPSS) version 25.0 (IL, USA). The statistical significance level will be for a p-value < 0.05. The distribution of data normality will be evaluated by Kolmogorov-Smirnov or Shapiro-Wilk tests. Continuous variables will be expressed as mean and standard deviation or median and interquartile range. Categorical variables will be expressed as frequency and percentage. Univariable analysis will be performed using the Kruskal-Wallis test or Anova test (continuous variables) and Qui-squared test test (categorical variables). The Wilcoxon or Friedman test and the t-Student or Anova test will be used to compare paired data. Cox regression multivariable analysis will be used to determine the independent factors associated with exocrine and endocrine pancreatic insufficiencies. Analysis of PERT efficacy will be performed per-Protocol (PP), excluding loss of follow-up and PERT non-compliance. The temporal evaluation of EPI and PERT response will be evaluated through Kaplan-Meier survival curves. The genome sequences will be grouped in OTU according to their similarity. The alpha taxonomic richness and diversity of stool samples will be expressed in observed species and Shannon index. The composition of fecal microbiota will be expressed in rarefaction curves and comparison of the differences in OTU richness with the t-Welch test. Immunological findings will be expressed by radar charts and representative FACS dot-plots. Additional statistical analysis will be defined a posteriori.

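### The immune sample at acute pancreatitis diagnosis is compared by severity and later EPI with no stated account of hours since symptom onset, so presentation time could pass for an immune difference

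*Combined protocol and SAP*

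**What the plan says.** Section D.3, Phase 4, sets three immune time points: "immunological status (at the diagnosis of acute pancreatitis, EPI and after PERT". The panel is flow-cytometry cell populations together with "cytokines, chemokines and growth factors by xMAP/Luminex". Entry under Phase 1 requires a definitive diagnosis by the revised Atlanta criteria. Neither the inclusion nor the exclusion criteria limit the time since symptoms began, and no section mentions symptom onset or a window for the first blood draw.

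Two objectives use the first sample observationally. A secondary objective is "To evaluate immunological changes according to acute pancreatitis severity". A primary objective is "To assess changes in immunologic response in EPI following acute pancreatitis and response to PERT", which takes in the comparison of patients who do and do not go on to EPI.

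For the analysis, section D.4 states "Univariable analysis will be performed using the Kruskal-Wallis test or Anova test (continuous variables" and, specifically for this panel, "Immunological findings will be expressed by radar charts and representative FACS dot-plots". It also lists tests for paired data and a multivariable Cox model for factors associated with exocrine and endocrine insufficiency, whose covariates are not named. Further analysis is left to be decided after the data are in.

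The Literature review attaches times to markers of this kind. An IL-6 cut-off is given for values "in the first 48 hours", three other proteins are cited at admission, and the group's own earlier predictors were taken "at admission of patients and within the first 24 hours of hospitalization".

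**The concern.** Two patients sampled at diagnosis can be at different stages of the acute response if one came to hospital soon after onset and the other a day later. If a marker rises or falls over those hours, its value mixes disease biology with delay. Severity and EPI status are not randomised, so nothing in the design balances delay between the groups. If patients with severe disease, or those who later have EPI, tend to arrive earlier or later than the rest, an unadjusted test attributes the resulting shift to severity or EPI. If the groups arrive at similar times there is no such bias, but the spread in timing still widens the variance and costs power.

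The timing matters for trial conduct. A covariate can be added to a model at any stage, but an onset time that was not asked about at admission is hard to reconstruct months later.

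**Working it through.** **The plan's own figure.** The only design figure is the sample size: 25% prevalence, 10% sampling error, 95% confidence, 10% drop-out. The single-proportion formula gives n = 1.96² × 0.25 × 0.75 / 0.10² = 72.03, rounded up to 73. Halved and rounded up this is 37 per arm, and 37 / 0.90 = 41.1, so 42 per arm and 84 in total, as stated. These are the PERT and placebo arms, all of whom have EPI. The figure gives no group sizes for comparisons by severity or by EPI status.

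**Inputs for the illustration, all assumed.**
- The marker declines exponentially with half-life h = 24 h (varied from 12 to 48 h). A rising marker gives the same size with the opposite sign.
- The SD of the log marker is 1.
- The groups differ by Δ hours in mean time since onset, with Δ = 0, 3, 6 or 12.
- There is no true immune difference, and the test is two-sided at 0.05 (D.4 gives the level but not the sidedness).
- Splits: 84 patients as 21 v 63 (25% v 75%, using the plan's prevalence), and 42 v 42 as an equal split of the same total.

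**Formulas.** The ratio of levels is 2^(−Δ/h). The log difference is δ = 0.693 × Δ/h. The noncentrality is δ / √(1/n₁ + 1/n₂), where the root is 0.252 for 21 v 63 and 0.218 for 42 v 42. The rejection probability comes from the noncentral t with 82 degrees of freedom (critical value 1.989).

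**Results at h = 24 h.**

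| Gap Δ | Ratio | δ | 21 v 63 | 42 v 42 |
|---|---|---|---|---|
| 0 h | 1.00 | 0 | 5% | 5% |
| 3 h | 0.92 | 0.087 | 6% | 7% |
| 6 h | 0.84 | 0.173 | 10% | 12% |
| 12 h | 0.71 | 0.347 | 27% | 35% |

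For the 12 h gap and 21 v 63, the noncentrality is 0.347 / 0.252 = 1.38, which gives 27%.

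**Sensitivity to half-life.** With a 12 h gap and half-lives of 12, 24 and 48 h, the rates are 78%, 27% and 10% (21 v 63), or 88%, 35% and 12% (42 v 42).

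**Sensitivity to cohort size.** If 84 EPI cases arose at 25% prevalence, the cohort would be 84 / 0.25 = 336, split 84 v 252. The 12 h gap at a 24 h half-life then gives 78%. A larger cohort makes a fixed bias easier to declare significant.

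**Does adjustment work?** A second parameterisation used the correlation ρ between marker and time since onset, and a gap d in SD units, again at 21 v 63. At d = 0.5 the unadjusted rate is about 9%, 17% and 28% for ρ = 0.3, 0.5 and 0.7. Over d = 0.25 to 0.75 and the same ρ it runs from 6% to 55%. In 4,000 simulated trials at d = 0.5, with time since onset as a covariate, the rate was 5.1%, 5.0% and 4.9%. With d = 0 the unadjusted rate was 5.1%.

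**The case against.** The strongest reply is that the documents contain no evidence of imbalance. Nothing in them suggests that severe cases, or later EPI cases, arrive at different times, and with no gap the false-positive rate is 5%. That stands, and it makes this a conditional risk.

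A reader might infer that onset time will not be recorded. The text does not show that. It contains no case-report form or variable list, and it refers to a Task 1 (EPI diagnosis and stratification) that is not included. What can be said is that recording is not specified.

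A reader might also infer that D.4 has no adjusted analysis at all. It has paired tests, which suit the repeated samples, and a Cox model for EPI. Since the Cox covariates are unnamed, the model may or may not include immune markers or timing. The concern is therefore weaker for EPI than for severity, which that model does not address.

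It is tempting to read the Literature review as fixing a 48-hour window from onset. It does not say where its 48 hours start, and its other anchors are admission and hospitalisation, which are close to the anchor the plan uses.

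Finally, for an admission biomarker the raw value at presentation may be what the clinician wants. That is a fair choice of estimand. It supports showing both estimates, but it does not support the unadjusted one alone when the stated aim is immune change by severity or EPI.

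**Conclusion.** The point holds as a cheap improvement to the observational comparisons of the first immune sample, by severity and by later EPI. As written, these could confound time of presentation with an immune difference, and they carry avoidable noise.

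The size cannot be determined from the documents. Every rate above rests on an assumed gap, half-life, log-SD and split, and the range properly starts at 5%, meaning no inflation. The single-exponential decline has no basis in the documents for the flow-cytometry populations and ratios.

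A reader might conclude that the immune primary objective as a whole is biased, or that 35% is this trial's false-positive rate. Neither follows. The samples at EPI diagnosis and after PERT lie outside the acute admission sample, the randomised contrast is unaffected in expectation, and 42 per group is the size of the randomised arms, which are not the groups compared here.

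**What to change.** 1. Record the date and time of symptom onset and of the first blood draw.
2. In D.4, compare the admission immune markers (log-transformed where skewed) by severity and by EPI status with hours since onset as a covariate, and report this alongside the unadjusted comparison.
3. If immune markers enter the Cox model for EPI, include hours since onset there as well.
4. Optionally, add a sensitivity analysis limited to early samples. The investigators should set its cut-off in advance, because the cited 48 hours are not stated to run from onset.

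The cost is two data fields and one degree of freedom per model, with no extra samples. Onset time is self-reported, so adjustment will be imperfect. Late presenters would drop out of the optional sensitivity analysis. The adjusted estimate also answers a slightly different question from the raw value at presentation, which is why both should be shown.

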#### D.4. Statistical analysis

Using of Statistical Package for the Social Sciences (SPSS) version 25.0 (IL, USA). The statistical significance level will be for a p-value < 0.05. The distribution of data normality will be evaluated by Kolmogorov-Smirnov or Shapiro-Wilk tests. Continuous variables will be expressed as mean and standard deviation or median and interquartile range. Categorical variables will be expressed as frequency and percentage. Univariable analysis will be performed using the Kruskal-Wallis test or Anova test (continuous variables) and Qui-squared test test (categorical variables). The Wilcoxon or Friedman test and the t-Student or Anova test will be used to compare paired data. Cox regression multivariable analysis will be used to determine the independent factors associated with exocrine and endocrine pancreatic insufficiencies. Analysis of PERT efficacy will be performed per-Protocol (PP), excluding loss of follow-up and PERT non-compliance. The temporal evaluation of EPI and PERT response will be evaluated through Kaplan-Meier survival curves. The genome sequences will be grouped in OTU according to their similarity. The alpha taxonomic richness and diversity of stool samples will be expressed in observed species and Shannon index. The composition of fecal microbiota will be expressed in rarefaction curves and comparison of the differences in OTU richness with the t-Welch test. Immunological findings will be expressed by radar charts and representative FACS dot-plots. Additional statistical analysis will be defined a posteriori.

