##### D.3. Study design

This project will take place in 4 distinct phases:

Phase 1: Recruitment of patients with acute pancreatitis and stratification of them according to the severity of acute pancreatitis and development of EPI (12-month follow-up).

All patients admitted to the Gastroenterology Department of Coimbra Hospital and University Centre by the first episode of acute pancreatitis will be included, consecutively, according to the revised Atlanta criteria 2012 and taking into account the inclusion/exclusion criteria and the minimum number of patients needed to obtain statistical power.

Inclusion criteria: Definitive diagnosis of acute pancreatitis, according to revised Atlanta criteria 2012.4

Exclusion criteria: Age <18years; History of allergy, hypersensitivity or contraindication to use of PERT; Prior acute pancreatitis; Other causes that may occur with EPI, including celiac disease, diabetic gastroparesis, chronic pancreatitis, cystic fibrosis, pancreatic neoplasia, ampuloma, somatostatinoma, somatostatin analog therapy, small bowel pathology, inflammatory bowel disease, and rare diseases associated with exocrine pancreatic insufficiency (Zollinger-Ellison syndrome, Shwachman-Diamond syndrome, Johanson-Blizzard syndrome); Prior gastrointestinal or pancreatic surgery or endoscopic/surgical therapy for obesity; medication with orlistat or acarbose; Respiratory pathology (severe chronic obstructive pulmonary disease), hepatic (Child-Pugh C cirrhosis) or biliary (obstructive jaundice) severe pathology; Non-compliance for PERT (when indicated); Uncontrolled thyroid pathology; Refusal/incapacity to give informed consent; and Follow-up period <12months after acute pancreatitis diagnosis.

Sample size calculation: For an estimated prevalence of EPI in the adult population of 25% and a drop-out rate of 10%, it was determined that for a 95% confidence level and 10% sampling error, it will be necessary to include 42 patients in each of the therapeutic arms (PERT vs placebo), making a total of 84 patients.

Diagnosis of EPI and stratification of patients: See Task 1.

Phase 2: Double-blind randomized placebo-controlled trial for patients with EPI after acute pancreatitis for PERT and collection of stool and blood samples before and after

PERT/placebo (6 months post-randomization).

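### D.4 ties no continuous-outcome test to PERT versus placebo and names no baseline-adjusted between-arm model, although pre-treatment values are collected and adjusting for them could add precision

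*Combined protocol and SAP*

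**What the plan says.** D.4 (Statistical analysis) gives a general list of methods.

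- Continuous variables: "Univariable analysis will be performed using the Kruskal-Wallis test or Anova test (continuous variables". No groups, outcome or covariate are named.
- Repeated values: "The Wilcoxon or Friedman test and the t-Student or Anova test will be used to compare paired data".
- Microbiota: "comparison of the differences in OTU richness with the t-Welch test". The groups are again not named.
- PERT is named in two sentences only: "Analysis of PERT efficacy will be performed per-Protocol (PP), excluding loss of follow-up and PERT non-compliance" and "The temporal evaluation of EPI and PERT response will be evaluated through Kaplan-Meier survival curves". The first sets the analysis population and the second covers time to response. Neither names a comparison of a continuous outcome.
- The one multivariable model is a Cox regression for factors associated with exocrine and endocrine insufficiency, not for the treatment effect.
- The rest is left open: "Additional statistical analysis will be defined a posteriori".

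The baseline data exist. D.3, Phase 2, provides for "collection of stool and blood samples before and after" PERT or placebo. Phases 3 and 4 place the microbiota, quality-of-life and immunological assessments at EPI diagnosis as well as after PERT. Section B lists PERT efficacy and the microbiota, immunological and quality-of-life responses to PERT as primary objectives.

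**The concern.** Many of the outcomes behind those primary objectives are continuous: Shannon index, observed species, cytokines, cell populations, SF-36 and QLC-C30 scores. For none of them can a reader of D.4 tell which comparison will estimate the PERT effect. Two things are at stake.

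**Precision.** With 42 patients per arm before losses, a between-arm comparison that ignores a measured baseline may give up information already collected.

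**Interpretation.** The Abstract expects EPI prevalence to decrease during follow-up, so some change over six months is plausible without PERT. A change within the PERT arm therefore does not estimate the PERT effect. If the between-arm estimate is not named in advance, nothing in D.4 prevents a paired result from being read that way.

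**Working it through.** **1. The plan's own sample size.** Inputs from D.3, Phase 1: prevalence 25%, 95% confidence, 10% sampling error, 10% drop-out. A one-proportion precision formula reproduces the stated total:

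- n = 1.96² × 0.25 × 0.75 / 0.10² = 72.03, rounded up to 73.
- Split over two arms: 36.5, rounded up to 37.
- Drop-out: 37 / 0.9 = 41.1, rounded up to 42 per arm, so 84.

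This calculation contains no between-arm effect, SD or power. Power for the continuous outcomes therefore has to be illustrated from assumptions.

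**2. Inputs for the illustration.**

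- From the plan: 42 per arm, 10% drop-out and significance at 0.05 (two-sided assumed). Completers: 42 × 0.9 = 37.8, taken as 38.
- Assumed, because the documents give neither: a true difference d = 0.5 SD, and a correlation ρ between the baseline and 6-month values of 0 to 0.7.

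**3. Formulas (noncentral t, n per arm).**

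- Unadjusted: noncentrality d / √(2/n), df 2n − 2. With n = 38: 0.5 / 0.2294 = 2.18, power 0.576.
- Baseline-adjusted: replace d by d / √(1 − ρ²), df 2n − 3. At ρ = 0.5: 0.5 / 0.866 = 0.577, noncentrality 2.52, power 0.700.
- Change score: replace d by d / √(2(1 − ρ)), df 2n − 2. At ρ = 0.7: 0.5 / 0.775 = 0.645, power 0.793.
- 95% CI half-width in SD: t × √(2/n) unadjusted, t × √(2(1 − ρ²)/n) adjusted.

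**4. Results, 38 per arm.**

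| ρ | Unadjusted power | Adjusted power | Adjusted CI half-width (unadjusted 0.457 SD) |
|---|---|---|---|
| 0 | 0.576 | 0.576 | 0.457 |
| 0.2 | 0.576 | 0.593 | 0.448 |
| 0.3 | 0.576 | 0.616 | 0.436 |
| 0.5 | 0.576 | 0.700 | 0.396 |
| 0.7 | 0.576 | 0.853 | 0.327 |

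If the unstated comparator were a change score, power would be 0.576 at ρ = 0.5 and 0.793 at ρ = 0.7. The step to adjustment is then 58% to 70%, or 79% to 85%.

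**5. Sensitivity to n.** With 37 per arm, unadjusted power is 56%. The per-protocol set also removes non-compliant patients. If an assumed 10% or 20% more are lost (42 × 0.9 × 0.9 = 34.0; 42 × 0.9 × 0.8 = 30.2), unadjusted power is 53% or 48%. Adjusted power at ρ = 0.5 is then 65% or 59%.

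**6. Price of adjusting.** One degree of freedom. With 74 completers and ρ = 0, the variance rises by about 1/(74 − 4) = 1.4%. The break-even correlation is about √(1/71) = 0.12.

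**7. Simulation.** With 20,000 trials at 38 per arm, adjusted power was 0.576, 0.589, 0.610, 0.698 and 0.848 at ρ = 0, 0.2, 0.3, 0.5 and 0.7. Type I error was 0.047 to 0.052 across both methods. The simulated arms were complete and randomised, so this says nothing about a set with exclusions after randomisation.

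**The case against.** **The listed tests may already cover the arms.** Kruskal-Wallis, ANOVA and Welch's test can each compare two arms. The ANOVA for paired data could be a repeated-measures model with arm as a factor, and the Welch test of differences could mean pre-post differences, though differences between groups is the plainer reading. This stands. A reader might infer that D.4 uses baseline values only within patients, or that efficacy will be judged by change within the PERT arm. The text is too vague to support either, and the design is plainly PERT against placebo. What remains is that no comparison is named and none is stated to be baseline-adjusted.

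**The gain is not assured.** This also stands. Nothing in the documents places these outcomes at a correlation of 0.5 or above, and values may differ between microbiota, cytokine, nutritional and quality-of-life measures. At 0.3 the gain is four percentage points. The illustration also assumes normally distributed outcomes, whereas D.4 keeps a rank-based route.

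**Validity of the per-protocol comparison.** A reader might take the simulated 5% error rate to show that the planned comparison is unbiased, with or without adjustment. It does not. Exclusions for non-compliance and loss to follow-up occur after randomisation, and baseline adjustment does not repair that.

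**Missing text.** D.3 says "Diagnosis of EPI and stratification of patients: See Task 1", and Task 1 is not in the supplied document. That pointer concerns diagnosis and stratification, not analysis, but other task-level detail may exist. The point is therefore limited to D.4 as supplied.

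**Conclusion.** The point holds as a gap in specification with an inexpensive improvement attached. It does not show that the listed tests are invalid. As supplied, D.4 does not say how PERT and placebo will be compared on continuous outcomes, and it names no between-arm model using the collected baseline.

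The size of the benefit rests on an assumed 0.5 SD effect, 38 completers per arm and an unknown correlation. It is negligible at 0.2 or below and material from about 0.5. No figure can be put on the risk of misreading a within-arm change, because the documents give no expected recovery size for these outcomes. The change should be made. Confidence is medium, because the wording of D.4 allows more than one reading and the correlations are assumed.

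**What to change.** Add to D.4:

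- The PERT effect on each continuous outcome is the between-arm difference at 6 months. It is estimated by a linear model with arm and the last pre-randomisation value of that outcome, and reported with a 95% CI.
- Nutritional markers, SF-36, QLC-C30, Shannon index and observed species are reported as differences in means. Skewed markers such as cytokines are analysed on the log scale at both time points and reported as ratios of geometric means. Where no transformation is suitable, a rank-based ANCOVA is used. The scale for each outcome is fixed in advance.
- For PERT response, paired within-arm tests are descriptive only. They remain suitable for the longitudinal cohort.

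The cost is a few sentences, slightly more analysis work and one degree of freedom; no new data are needed. Three rules must be written: the scale for each outcome, the handling of zero or undetectable values before taking logs, and the handling of a missing pre-randomisation value. The change does not settle the primary outcome, multiplicity or the per-protocol-only analysis set, which need separate decisions.
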